A Comparative Study between Dissociative Treatment and Binocular Interactive Treatment in Amblyopia

Thesis

Submitted to Faculty of Medicine – Ain Shams University
In Partial Fulfillment of the Requirements of Doctorate Degree in Ophthalmology
By

[name]

M.B,B.C.h (2009) , M.Sc (2014) ,

Faculty of medicine - Ain Shams University

Under supervision of

[name]. [name]

Professor of Ophthalmology
Faculty of medicine – Ain Shams University

[name]. [name]

Professor of Ophthalmology
Faculty of medicine – Ain Shams University

[name] [name]

Lecturer of Ophthalmology
Faculty of medicine – Ain Shams University

[name] [name]

Lecturer of Ophthalmology
Faculty of medicine – Ain Shams University

Faculty of medicine
Ain Shams University
Cairo – Egypt
2017

STATISTICAL ANALYSIS PLAN

Using the SPSS (or the Minitab or Mega Stat) statistical software, the data will be examined using standard summary statistics which will include, where appropriate, 95% confidence intervals.

A one-way analysis of variance (ANOVA) will be performed on the visual acuity data to determine whether there appeared to be an effect of measurement time on visual acuity, and pairwise comparisons of mean will then be performed, examining the changes from baseline to 1 month, 3 months and 6 months after treatment start.

An improvement of ≥ 0.125 LogMAR units will be considered clinically significant. In addition, the proportion of change will be calculated at 1 month, 3 months and 6 months follow up as follows (using the formula described by Stewart et al)

$$\text{Proportion of change} = \frac{VA_{as} - VA_{ae}}{VA_{as} - VA_{fe}}$$

Where VA_{as} is the vision of amblyopic eye at baseline, VA_{ae} is the vision of amblyopic eye at the end of the treatment (i.e. 6months) and VA_{fe} is the vision of the non-amblyopic eye at the end of the treatment.

Also percentage of compliance with treatment in each group will be measured as a secondary outcome measure.

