A step further to conventional treatment is the use of a home-based approach allowing remote internet monitoring of treatment between office visits and hence better compliance. **(Hess et al., 2014)** In addition a video game version of the treatment is developed to make it more enjoyable for improving compliance. **(Foss et al., 2013)**. Moreover, dichoptic presentation can be achieved on the iPod device using a lenticular overlay screen. The advantage of using a lenticular overlay screen is that the luminance contrast is preserved **(Hess et al.; 2014)**

Aim of the work:

The aim of this work is to compare the gold standard occlusion therapy alone with dichoptic therapy

Patients and Methods:

Design:

The study will be a prospective experimental controlled study.

Patients of the study:

From the vicinity of the ophthalmology outpatient clinic of Ain Shams University Hospital, 100 patients of both sexes with amblyopia will be enrolled to this study. Informed consents will be obtained from adult patients and children's parents.

Patients will be assigned randomly into two groups:

Group A: 50 patients will receive the gold standard occlusion therapy

Group B: 50 patients will receive dichoptic treatment in the form of playing a video game (Lazy Eye Tetris games such as Lazy Eye Blocks ®) while wearing a red/green goggle.

Each group will be subdivided according to age:

1. From 4 to 7 years.
2. From above 7 to 12 years.
3. From above 12 to 30 years.

Hours of occlusion will be classified according to the degree of amblyopia:

- Mild to moderate amblyopia (Best corrected visual acuity (BCVA) < 0.2): 2-4 hours occlusion
- Severe (BCVA > 0.2): 4-6 hours occlusion

Hours of dichoptic treatment in group B will be classified according to the degree of amblyopia:

- Mild to moderate amblyopia (BCVA < 0.2): 2-4 hours of treatment
- Severe (BCVA > 0.2): 4-6 hours of treatment

Inclusion Criteria:

- Any degree of amblyopia
- Orthotropia in primary position.

Exclusion Criteria:

- Any ocular disease affecting vision
- Angle of deviation in primary position (Heterotropia)
- Adult patients and children's parents unwilling to enter or complete the study
- Ignorance of patients to use the video game

Methods

All patients will undergo the following:

- 1) Full medical and ophthalmic history
- 2) Examination:
 - A) External Appearance:
Anomalous Head Posture, globes (e.g., proptosis), lids (e.g. ptosis).
 - B) Refraction:
With and without cycloplegia.

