 - C) Visual acuity:
With and without correction using Snellen acuity chart and preferential looking test for non-verbal patients.
 - D) Motility:
Ductions and versions (9 positions of gaze)
 - E) Angle of deviation if any
 - F) Fixation :
Fixation behavior (fixation preference) will be tested via base down 10 PD fixation preference test.
 - G) Quantitative Binocular vision assessment
 - H) Anterior segment examination.
 - I) Posterior segment examination using indirect ophthalmoscopy with a 20-D (diopter) lens through a dilated pupil.

All patients in Group A will receive the gold standard occlusion therapy. All patients in Group B will receive dichoptic treatment

Treatment assessment:

All patients will be followed up in the following schedule: after 1 month, after 2 months and after 6 months with regards to visual acuity. Patients who fail to complete the full time of the follow up period will be excluded from the study.

References:

- 2) Aldebasi YH. Prevalence of amblyopia in primary school children in Qassim province, Kingdom of Saudi Arabia. *Middle East Afr J Ophthalmol.* 2015;**22**(1):86-91
- 3) American Academy of Ophthalmology Basic and Clinical Science Course Subcommittee. Basic and Clinical Science Course. Pediatric Ophthalmology and Strabismus: Section 6. San Francisco, CA: American Academy of Ophthalmology. 2012.pp.61.
- 7) Birch EE. Amblyopia and binocular vision. *Progress in retinal and eye research* 2013;**33**:67-84

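### The SAP tests change over visits with a one-way ANOVA although the same patients are measured each time; run as written, the test is conservative and loses power

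*SAP*

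**What the plan says.** The second paragraph of the statistical analysis plan names the test: "A one-way analysis of variance (ANOVA) will be performed on the visual acuity data". Its purpose is "to determine whether there appeared to be an effect of measurement time on visual acuity", so time is the factor. Pairwise comparisons of means follow, "examining the changes from baseline to 1 month, 3 months and 6 months after treatment start". With baseline, that makes four levels.

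The protocol, under Treatment assessment, has all patients seen "after 1 month, after 2 months and after 6 months with regards to visual acuity", and adds: "Patients who fail to complete the full time of the follow up period will be excluded from the study". Under Patients of the study, "100 patients of both sexes with amblyopia will be enrolled to this study", 50 in each group.

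Neither document refers to repeated measures, a patient effect, paired tests or sphericity. The SAP does not say whether the ANOVA is run within each arm or on all 100 patients, or whether the pairwise comparisons are paired.

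**The concern.** Time is a within-patient factor here: every analysed patient contributes to every level. A one-way ANOVA assumes that the levels hold different, independent subjects. Its error term therefore contains the differences between patients, which cancel when each patient is compared with himself or herself. Acuity in the same eye over six months should be positively correlated, so the error term is too large, F too small and the p-value too large.

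At stake is sensitivity. This is the only significance test that the SAP names. It could miss a change of the size in the SAP's own threshold ("An improvement of ≥ 0.125 LogMAR units will be considered clinically significant"), mainly if it is run arm by arm. If the pairwise comparisons are also unpaired, the confidence intervals for change from baseline are too wide as well.

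**Working it through.** The documents state no alpha, SD, within-patient correlation or power, so there is no figure of the plan's to reproduce.

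**Inputs from the documents:** four visits; n = 50 per arm or n = 100 pooled; 0.125 logMAR as the size of change. The SAP gives 0.125 as a threshold of clinical significance, not as a design effect; it is used here as a mean change for illustration.

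**Assumptions:** alpha 0.05 (in line with the SAP's 95% intervals); SD 0.20 to 0.35 logMAR; correlation ρ mostly 0.5 or 0.7; mean acuity 0.50, 0.46, 0.42, 0.375 over the four visits.

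**Step 1, direction.** With equal correlation ρ between all visits (compound symmetry) and no true change, the time mean square has expectation σ²(1−ρ), while the one-way error mean square has expectation σ². F is therefore shrunk by about (1−ρ), and the true size is about P[F(3, 4(n−1)) > Fcrit/(1−ρ)]. For n = 50, Fcrit = 2.651 on 3 and 196 df:

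- ρ = 0: size 5%
- ρ = 0.3: 2.651/0.7 = 3.79, size 1.1%
- ρ = 0.5: 2.651/0.5 = 5.30, size 0.16%
- ρ = 0.7: 2.651/0.3 = 8.84, size about 0.002%

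Simulation agrees: about 5% at ρ = 0, 1.1% at 0.3 and 0.2% at 0.5. The Greenhouse-Geisser repeated-measures test stays between 4% and 5.5% throughout.

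**Step 2, power of the overall test** (simulated, compound symmetry; one-way against Greenhouse-Geisser repeated measures):

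| n | SD | ρ | One-way | Repeated measures |
|---|---|---|---|---|
| 50 | 0.20 | 0.5 | 81% | 98% |
| 50 | 0.25 | 0.5 | 49% | 88% |
| 50 | 0.25 | 0.7 | 45% | 99% |
| 50 | 0.30 | 0.5 | 28% | 72% |
| 100 | 0.20 | 0.5 | over 99% | over 99% |
| 100 | 0.25 | 0.5 | 93% | over 99% |
| 100 | 0.25 | 0.7 | 96% | 100% |
| 100 | 0.30 | 0.5 | 74% | 97% |
| 100 | 0.35 | 0.5 | 52% | 89% |

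**Step 3, sensitivity to the correlation pattern.** Under AR(1), where correlation fades as visits grow further apart, with SD 0.25 and adjacent-visit correlation 0.5 or 0.7:

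- n = 50: about 49% against 69% (0.5), and about 46% against 82% (0.7)
- n = 100: 86% against 94% (0.5), and 88% against 99% (0.7)
- n = 50, no true change, correlation 0.5: the one-way test rejects about 1% of the time

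The direction is unchanged and the loss is smaller.

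**Step 4, pairwise comparisons, only if they are unpaired.** The ratio of standard errors is √(2σ²/n) / √(2σ²(1−ρ)/n) = 1/√(1−ρ), which is 1.41 at ρ = 0.5 and 1.83 at ρ = 0.7, where ρ is the correlation between the two visits compared. At n = 50 and SD 0.25 the 95% half-widths are:

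- unpaired, pooled error: 1.972 × 0.25 × √(2/50) = 0.099 logMAR
- paired, ρ = 0.5: 2.010 × 0.25 × √(2 × 0.5/50) = 0.071
- paired, ρ = 0.7: 2.010 × 0.25 × √(2 × 0.3/50) = 0.055

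Simulated power for baseline to 6 months is 77% against 93% (ρ = 0.5) and 83% against 99% (ρ = 0.7). If correlation fades over six months, this widening is smaller.

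**The case against.** The strongest reply is that one-way may be shorthand for a one-way repeated-measures ANOVA, since the single factor is time and the plan then speaks of changes from baseline. That is possible. But the SAP does not say so, and it leaves the choice open among three packages; an analyst who takes the named procedure literally would run the independent-groups test. If repeated measures was meant, the repair is a few words.

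Second, the pairwise comparisons do not depend on a significant F. If they are paired, only the overall test is affected and the changes from baseline are still estimated properly. This stands, and it limits the harm.

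Third, a test of time is a before-after question, whereas the protocol's aim is to compare two treatments. A conservative test of time makes no false claim about either. This also stands: the lack of a between-arm test is a separate and more serious gap, and this point takes no weight from it.

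Fourth, the size depends on SD, correlation and correlation pattern, none of which is documented. Under AR(1) at 0.5, the one-arm loss at SD 0.25 is about 20 percentage points (69 − 49) instead of 39 (88 − 49). The figures are therefore ranges. The direction held in every setting with positive correlation.

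**Conclusion.** The concern holds. As written, the named test has the wrong error term for these data. The consequence is lost power for the overall test of time, with no excess of false positives. Run per arm at SD 0.25, power of about 45% to 49% compares with 69% to 99% for a repeated-measures analysis, across correlations of 0.5 and 0.7 and both patterns. Run on all 100 patients, the loss is negligible at SD 0.20, modest at SD 0.25 and material from SD 0.30 upward. Intervals for change are affected only if the contrasts are unpaired. The direction requires only positive correlation between visits; the magnitudes rest on the assumed SD, correlation, mean path and alpha. The plan should be corrected, but the error cannot manufacture a positive result.

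**What to change.** Replace the one-way ANOVA with a repeated-measures analysis of amblyopic-eye logMAR acuity. Either a repeated-measures ANOVA with Greenhouse-Geisser correction or a mixed model with unstructured within-patient covariance will do. The sphericity correction matters: uncorrected, the repeated-measures F rejected up to about 7% under AR(1).

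- Include visit, group and group-by-visit terms, which also settles whether the analysis is per arm or pooled.
- Keep baseline as one of the outcome visits, and do not enter it again as a covariate.
- Report changes from baseline as within-patient (paired) contrasts with 95% confidence intervals.
- Reconcile the protocol's 2-month visit with the SAP's 3-month visit before defining the visit factor.
- State how acuities recorded on the Snellen chart are converted to logMAR.

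The cost is SAP wording and slightly more analysis work. No new data are needed, and the visit discrepancy has to be resolved in any case.

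### The SAP tests acuity over time only; no comparison of the two randomised treatments is specified for any outcome

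*SAP*

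**What the plan says.** The protocol, under Aim of the work, gives one aim in the text available: "The aim of this work is to compare the gold standard occlusion therapy alone with dichoptic therapy". Under Patients of the study it adds "100 patients of both sexes with amblyopia will be enrolled to this study" and "Patients will be assigned randomly into two groups", with 50 in each group.

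The SAP names two inferential procedures, both in its second paragraph. The first is a one-way ANOVA of visual acuity "to determine whether there appeared to be an effect of measurement time on visual acuity". The second follows in the same sentence: "pairwise comparisons of mean will then be performed, examining the changes from baseline to 1 month, 3 months and 6 months after treatment start".

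The rest of the SAP is descriptive. Its first paragraph promises "standard summary statistics which will include, where appropriate, 95% confidence intervals". Its third sets a threshold for improvement ("0.125 LogMAR units will be considered clinically significant") and defines a proportion of change at each visit. The last says that the "percentage of compliance with treatment in each group will be measured as a secondary outcome measure". The protocol's Methods and Treatment assessment sections add no statistical method.

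**The concern.** The trial exists to compare two treatments, yet treatment group is not a factor in either named test. A one-way ANOVA has a single factor, and here that factor is measurement time. The SAP does not say whether the ANOVA pools the groups or is run in each group, and neither reading tests the treatment difference.

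- **Pooled:** the test follows the average gain of all 100 patients. It cannot separate two equal treatments from one good and one useless treatment with the same average.
- **Per group:** the likely reading of the results is that one group improved significantly and the other did not. That is not a test of the difference. How often the pattern appears depends on the size of the gains and on the test used, not only on whether the treatments differ.

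By-group means could still be tabulated, but any difference would be untested. If a comparison were added later, its outcome, visit and model would be chosen after the data were seen. Four measures (acuity, threshold, proportion of change, compliance) and three follow-up visits leave many possible choices.

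**Working it through.** **Step 1: text check, outcome by outcome.**

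| Outcome in the SAP | What is specified | Group A versus B test, term or interval |
|---|---|---|
| Visual acuity | One-way ANOVA on time; changes from baseline | None |
| Improvement of at least 0.125 logMAR | Threshold only | None |
| Proportion of change | Formula only | None |
| Compliance | Measured in each group | None |
| 95% intervals | Attached to summary statistics, where appropriate | No contrast named |

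The finding rests on this table. What follows only illustrates the consequence.

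**Step 2: inputs.** From the documents: 50 per group; visits at baseline, 1, 3 and 6 months (SAP); the figure 0.125 logMAR. The sample size of 100 cannot be reproduced, because no error rate, power, difference or SD is given for it. Assumed: logMAR SD 0.25; correlation 0.7 between any two visits; 0, 1/6, 1/2 and all of the 6-month gain reached at the four visits; two-sided 5%; 20,000 simulated trials per scenario. The SAP defines 0.125 as an improvement. Using it as a true difference between groups is a further assumption.

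**Step 3: groups pooled.** Percentage of trials rejecting:

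| True gains A/B | One-way ANOVA on time | Repeated-measures ANOVA on time | Baseline-adjusted group comparison |
|---|---|---|---|
| 0.125 / 0.125 | 97.3 | 100 | 5.3 |
| 0.0625 / 0.1875 | 97.0 | 100 | 93.2 |
| 0 / 0.25 | 95.8 | 100 | 100 |
| 0 / 0.125 | 8.2 | 82.3 | 93.1 |

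The first three rows share an average gain of 0.125, and the time test barely moves while the true difference goes from 0 to 0.25. In the last row the difference is 0.125, as in the second, but the average gain is halved and the time test falls.

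**Step 4: tests run per group, treatments equal.** If each group's test has power p, exactly one group is significant with probability 2p(1−p), which peaks at 50% when p = 0.5. For the paired baseline-to-6-month test:
- SD of change = 0.25 × √(2 × 0.3) = 0.194; SE = 0.194/√50 = 0.0274.
- A common gain of 0.05 gives 0.05/0.0274 = 1.83, so p is about 0.43 and 2 × 0.43 × 0.57 = 49%.

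| Common gain | Exactly one significant, one-way ANOVA | Exactly one significant, paired test |
|---|---|---|
| 0.05 | 0.9% | 49.1% |
| 0.10 | 31.0% | 9.5% |
| 0.125 | 50.2% | 1.2% |
| 0.20 | 0.8% | 0.0% |

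**Step 5: tests run per group, true difference always 0.125.**

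| True gains A/B | Exactly one significant, one-way ANOVA | Exactly one significant, paired test |
|---|---|---|
| 0 / 0.125 | 50.0% | 94.3% |
| 0.0625 / 0.1875 | 97.5% | 39.0% |
| 0.1375 / 0.2625 | 32.8% | 0.1% |
| 0.20 / 0.325 | 0.4% | 0.0% |

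The adjusted group comparison rejects in about 93% in all four rows.

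**Step 6: power of the candidate group comparisons for a difference of 0.125.** SE = √(2·v·SD²/n), with v = 1 − 0.7² = 0.51 for ANCOVA, 2(1 − 0.7) = 0.60 for mean change and 1 for final acuity alone. Forty analysed per group is an assumed allowance for dropout.

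| n per group | ANCOVA | Mean change | Final acuity alone |
|---|---|---|---|
| 50 | SE 0.0357, 93.4% | SE 0.0387, 89.2% | SE 0.0500, 69.7% |
| 40 | SE 0.0399, 87.1% | SE 0.0433, 81.4% | SE 0.0559, 59.8% |

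Over SD 0.20–0.30 and correlation 0.5–0.8, ANCOVA power runs from 66.3% to 99.9% (n = 50) and from 56.5% to 99.6% (n = 40). For mean change it runs from 54.1% to 99.8% and from 45.2% to 99.2%.

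**The case against.** The best defence is that the SAP is terse and the comparison is implied: the title calls the work comparative, the aim is comparative, and confidence intervals are promised. Pairwise comparisons of means might also be thought to cover the groups. This does not hold up. The sentence on pairwise comparisons ties them to changes from baseline, the intervals belong to summary statistics, and intent to compare does not specify an outcome, a visit or a model. The SAP text runs on without a redaction mark, so nothing removed explains the gap.

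Three narrower objections have substance.

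- **Independence of visits.** Some of the larger figures arise because a one-way ANOVA treats repeated visits as independent. With a repeated-measures test, the pooled 8.2% becomes 82.3%, and the per-group 50% at an equal gain of 0.125 becomes about 2%. That mixes in a second question, whether pairing is ignored. The conclusion survives: the repeated-measures test also follows the average gain, and the paired test still gives 49% at a common gain of 0.05.
- **Assumed values.** The 0.125 difference and the 40 analysed per group are not design values. The power figures help to choose among models and are not evidence of the gap.
- **Extent of the remedy.** One pre-specified acuity comparison closes the main gap. Group comparisons of the other outcomes are sensible secondary additions.

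**Conclusion.** The concern holds on the text alone and must be fixed. The SAP specifies no comparison of the randomised groups for any outcome, so the plan, followed exactly, does not test the protocol's stated aim. Under the assumed SD and correlation, the time tests can reject almost always when the treatments are equal (97% pooled). They can also be significant in exactly one group in about half of trials with equal treatments, or in under 1% when the true difference is 0.125. The exact percentages depend on the assumed SD, correlation and gains and on the test used. The conclusion that a time test does not estimate the treatment difference does not.

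**What to change.** **Required.** State as the main analysis the difference (Group B minus Group A) in 6-month amblyopic-eye logMAR acuity, adjusted for baseline acuity, with a 95% CI. ANCOVA is suitable. So is a repeated-measures model with a group-by-time term, reporting the 6-month contrast. Comparing mean change from baseline would also close the gap, with somewhat less power (89% against 93% under the assumptions above). The protocol's age bands may be added as a covariate.

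**Recommended as secondary.** Give a risk difference with 95% CI for the proportion improving by at least 0.125 logMAR, and group differences with 95% CI for the proportion of change and for compliance. Keep the time analysis as descriptive and say that it is run within each group.

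**Cost.** Plan wording only; group, age, and baseline and 6-month acuity are already collected. The wording should also cover two connected points. The protocol measures acuity by Snellen chart, or preferential looking in non-verbal patients, so a rule for obtaining logMAR values is needed. The protocol also drops patients who do not finish follow-up, so the analysis set for the 6-month comparison must be stated. The intermediate visit (2 months in the protocol, 3 in the SAP) needs reconciling but does not affect the 6-month contrast.

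### The SAP names no primary acuity measure, visit, alpha or multiplicity rule, and its three named, unadjusted comparisons test change over time, not the difference between treatments

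*SAP*

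**What the plan says.** The analysis plan is a few paragraphs in the SAP under Statistical Analysis Plan.

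- **Tests named.** A one-way ANOVA on acuity is meant "to determine whether there appeared to be an effect of measurement time on visual acuity". After it, "pairwise comparisons of mean will then be performed, examining the changes from baseline to 1 month, 3 months and 6 months after treatment start". The pairwise step is not made conditional on the ANOVA result, and no treatment factor is mentioned.
- **Clinical threshold.** "An improvement of ≥ 0.125 LogMAR units will be considered clinically significant". No visit, responder rate or test is attached.
- **Proportion of change.** The SAP says that "the proportion of change will be calculated at 1 month, 3 months and 6 months follow up", yet its formula uses the "vision of amblyopic eye at the end of the treatment (i.e. 6months"). No test is attached.
- **Ranking.** The only outcome with a rank is compliance: "percentage of compliance with treatment in each group will be measured as a secondary outcome measure".
- **Level.** No alpha or sidedness is given. The nearest statement is that summary statistics are to be ones "which will include, where appropriate, 95% confidence intervals".

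The protocol's Aim of the work is to compare occlusion with dichoptic therapy, with 50 patients randomised to each (Patients of the study). Its Treatment assessment section schedules acuity at 1, 2 and 6 months. The protocol names no primary outcome or time point either.

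**The concern.** Labelling one outcome secondary implies a primary one, but none is designated. Acuity can be read as a mean change, against the 0.125 LogMAR threshold or as a proportion of change, and at more than one visit. Nothing fixes which reading decides the trial, so the choice can be made after the data are seen. The tests that are named carry no adjustment.

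The contrast is open as well as the measure. The trial randomises two treatments in order to compare them, but the named acuity tests ask whether vision changes with time. A significant result from them would say nothing about which treatment does better, and whoever writes the report would have to choose a between-arm analysis at that stage.

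**Working it through.** The documents state no alpha, power, effect size or SD, so there is no figure of the plan's own to reproduce. Two-sided 5% per test is an assumption throughout.

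**1. Count the looks.** Mean change at three visits gives 3 named comparisons. Testing the proportion of change at its three visits would make 3 + 3 = 6. Testing the 0.125 LogMAR threshold once would make 7. Only if the threshold were also tested at every visit is the count 3 × 3 = 9. The text supports three tests. The rest are possible, not planned.

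**2. Error for the three named comparisons.** Each sets a visit against the same baseline. With equal variances and a common correlation r among the four measurements, each change has variance proportional to 2(1 − r) and any two changes have covariance proportional to 1 − r. The changes therefore correlate at 0.5 whatever r is. Independent tests would give 1 − 0.95³ = 14.3%, and the shared baseline lowers this. Null simulation with 50 patients (one arm) and 6,000 replicates gave:

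| Correlation r | Any of 3 paired tests, ungated | Same, only after a significant repeated-measures F-test |
|---|---|---|
| 0 | 12.5% | 4.0% |
| 0.5 | 12.3% | 4.0% |
| 0.8 | 12.4% | 3.9% |

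The Monte Carlo standard error at 12% is √(0.12 × 0.88 / 6,000) = 0.4 percentage points. If the three comparisons were run separately in each arm, which the SAP leaves open, the arms would be independent and the ungated figure would be about 1 − 0.88² = 23%.

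The gated 4% holds only when acuity changes at no visit. If it truly changes at one visit, the gate tends to open and the other two comparisons are unprotected, with error up to 1 − 0.95² = 9.75%.

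**3. Between-arm tests, if they were added.** The SAP contains none, so this is illustrative. Assumptions not in the documents: mean change 0.15 and SD 0.15 logMAR in both arms, interocular gap about 0.5 (SD 0.2) logMAR, and correlation between visits from 0 to 0.9. The proportion of change was approximated as change divided by the gap. With 50 per arm and 6,000 replicates, the chance of at least one false positive was:

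| Correlation between visits | 3 mean-change tests | 6 (plus proportion of change) | 9 (plus threshold) | One 6-month test |
|---|---|---|---|---|
| 0 | 15.0% | 21.4% | 28.4% | 4.9% |
| 0.3 | 13.5% | 19.9% | 26.4% | 5.0% |
| 0.5 | 12.4% | 18.1% | 25.2% | 4.9% |
| 0.7 | 10.6% | 15.1% | 21.7% | 4.6% |
| 0.9 | 8.5% | 12.5% | 18.4% | 4.9% |

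Independence would give 1 − 0.95⁹ = 37.0% for nine. That is too high, because all nine derive from the same acuity readings.

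**4. Set the tests against the aim.** Aim: difference between arms. ANOVA: effect of time. Pairwise comparisons: change from baseline. No named acuity test contains the contrast that the trial was randomised to estimate.

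**The case against.** The strongest defence is that the plan is simpler than the concern makes it. It names three comparisons, preceded by an omnibus test that may be meant as protection. Calling compliance secondary makes acuity the evident main domain, and the formula treats 6 months as the end of treatment.

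Part of this stands. Acuity is plainly the main domain, and a gated reading is possible; under it the global-null error is below 5%. But the SAP does not state the gate, and the gate would not cover the other two acuity quantities or any between-arm test. The 6-month phrase defines a term in a formula whose result is to be calculated at all three visits. It does not designate a primary time point.

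The 12% also describes a null of no change over time, which is not the expected state when both arms are treated. That weakens the error-rate argument for the named tests, but it makes more pressing the point that they do not address the aim.

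A reader might infer two stronger things that the documents do not support:

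- **That the plan contains nine tests with a 37% error rate.** Six of the nine would have to be supplied by the reader, and 37% assumes an independence that cannot hold. Conversely, repeating tests by arm or in the protocol's three age groups could take the count above nine, but no such tests are specified.
- **That any one of the planned looks could show one treatment to be better.** As written, none can, because none compares the arms.

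**Conclusion.** The concern holds in a limited form. Neither document fixes a primary acuity measure, time point, alpha or multiplicity rule. The three named comparisons are unadjusted and run at about 12% family-wise error if ungated, or about 4% under the global null with a repeated-measures gate that the SAP does not state. These figures rest on an assumed two-sided 5% per test and, for the simulation, equal correlation between measurements.

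The ranges of 9% to 15% for three between-arm tests and 18% to 28% for nine are illustrations of what could follow if such tests were added freely. They are not properties of the written plan. The more consequential defect needs no simulation: the planned acuity tests do not answer the comparative question. This should be corrected before the data are analysed.

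**What to change.** Name one primary analysis in the SAP: the between-arm difference in amblyopic-eye logMAR change from baseline to 6 months, tested two-sided at 5% and reported with a 95% CI. Six months is a visit in both documents. Then:

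- Make the earlier visits, the rate of improvement of at least 0.125 LogMAR, the proportion of change and compliance secondary. Either test them under a Holm correction or report estimates with CIs only.
- Report within-arm changes from baseline descriptively.
- State how Snellen acuity is converted to logMAR, and how non-verbal patients assessed by preferential looking (Protocol, Methods) enter the analysis.
- Reconcile the middle visit, which is 2 months in the protocol and 3 months in the SAP.

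The cost is SAP text, including a between-arm analysis and a conversion rule that are not there now, but no extra patients or visits. The downside is that earlier visits and derived measures can no longer carry a confirmatory claim on their own.

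The alternative of keeping all nine looks confirmatory is dearer. Bonferroni would set 0.05/9 = 0.0056 per test. For an illustrative between-arm difference of 0.125 logMAR (the SAP's threshold for improvement, borrowed only as an example), with 50 per arm and assumed SDs of 0.15, 0.20 and 0.25, power falls from 98.6%, 87.8% and 70.5% for a single test at 5% to 91.8%, 63.8% and 39.2%.
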